## 2. Study Objective

To evaluate the effectiveness of ultrasound-guided corticosteroid injections combined with rehabilitation, and to compare PNF-based therapy with conventional physiotherapy in improving pain, function, and quality of life in patients with subacromial bursitis.

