## 3. Study Design

Randomized controlled trial with two parallel groups (1:1 allocation).

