## 6. Outcome Measures

- Primary: Numeric Rating Scale (NRS)
- Secondary: DASH, EQ-5D-3L, EQ-VAS, Range of Motion (ROM)

Assessments at baseline, post-injection, post-rehabilitation, 3 months, and 6 months follow-up.

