## **7. Statistical Analysis**

Data will be analyzed using repeated measures ANOVA and independent t-tests. A p-value  $<0.05$  will be considered statistically significant.

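### Repeated measures ANOVA over five visits, with no missing-visit rule or sphericity correction, leaves room for a completers' comparison of PNF with conventional physiotherapy and an inflated group-by-time test; a mixed model avoids both at little cost

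*Combined protocol and SAP*

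**What the plan says.** Section 7 (Statistical Analysis) is two sentences long. The first names the methods: "Data will be analyzed using repeated measures ANOVA and independent t-tests". The second says that a p-value below 0.05 "will be considered statistically significant".

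Section 6 (Outcome Measures) makes pain on the NRS the primary outcome and lists the visits: "Assessments at baseline, post-injection, post-rehabilitation, 3 months, and 6 months follow-up". No visit is named as primary.

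Section 2 (Study Objective) has two parts: the effectiveness of injections combined with rehabilitation, and "to compare PNF-based therapy with conventional physiotherapy in improving pain, function, and quality of life". Section 5 (Intervention) gives both arms the same course of injections before the rehabilitation programmes diverge, each with 10 sessions over 2 weeks.

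The plan states no analysis set, no handling of missed visits and no sphericity correction. It does not say which ANOVA effect or which t-test decides the PNF comparison.

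**The concern.** Classical repeated measures ANOVA needs a value at every visit. One missed visit, even the last, removes the participant from the whole analysis, including the scores already recorded. With follow-up to 6 months after a two-week programme, some missed visits are likely. If those who stop attending differ in pain, and differ in another way in the other arm, the remaining participants no longer give the randomised comparison.

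The within-subject F-tests (time and group-by-time) also assume sphericity, meaning equal variances of the differences between any two visits. The visits here are weeks apart during treatment and months apart afterwards, so scores from neighbouring early visits will probably correlate more strongly than scores from distant ones. An uncorrected F-test then rejects too often.

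At stake is the test most likely to be read as the answer on PNF versus conventional physiotherapy.

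**Working it through.** The documents give no sample size, SD, correlation or expected dropout, so there is no figure of the plan's to reproduce. From the documents: five visits (four after baseline), two arms at 1:1, alpha 0.05 (taken as two-sided). Everything else below is an assumption.

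**1. Participants lost to listwise deletion.** If a proportion p misses each of the four post-baseline visits independently, the loss is 1 − (1 − p)^4.

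- p = 2%: 1 − 0.98^4 = 7.8%
- p = 5%: 1 − 0.95^4 = 18.5%
- p = 10%: 1 − 0.90^4 = 34.4%

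The cost in power, with an assumed 30 per arm and a standardised difference of 0.74: power is 0.82 with no loss, and 0.78, 0.73 and 0.67 at 10%, 20% and 30% loss.

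**2. Bias among completers.** Simulated with no true effect, 40 per arm, SD 2, correlation 0.6 and about 25–28% dropout depending on the last observed NRS. The ranges come from runs with somewhat different dropout models.

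| Dropout pattern | Bias at 6 months (NRS points) | False-positive rate, 6-month t-test |
|---|---|---|
| Pain-related in one arm only | about 0.3 (0.29–0.35) | 8–10% |
| Pain-related in opposite directions | 0.5–0.7 (0.54–0.70) | 16–27% |
| Same in both arms | about 0 | about 5% |

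An estimate using all observed visits had a bias of about 0.01 or less throughout.

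A hand check links the two columns. With 25% lost, 40 × 0.75 = 30 remain per arm, and the standard error of the difference is 2 × √(2/30) = 0.516. A bias of 0.30 is 0.30/0.516 = 0.58 standard errors, so the two-sided rejection rate is Φ(0.58 − 1.96) + Φ(−0.58 − 1.96) ≈ 0.084 + 0.006 = 9%. A bias of 0.54 (1.05 standard errors) gives about 18%, and 0.70 (1.36) gives about 27%.

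These rates belong to the 6-month t-test. In one run at 25% dropout, where that t-test rejected 8% (one arm) and 16% (opposite directions), the completers' group-by-time test rejected 6% and 10%, and the group main effect 10% and 29%.

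**3. Sphericity.** Null simulation with complete normal data, five visits, 20, 30 or 50 per arm and 20,000 trials per setting; the Monte Carlo standard error at 5% is √(0.05 × 0.95/20,000) = 0.0015. Epsilon = tr(A)² / [(k − 1) tr(A²)], where A is the doubly centred covariance matrix and k = 5.

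| Assumed covariance | Epsilon | Uncorrected group-by-time alpha |
|---|---|---|
| Compound symmetry, 0.5 | 1.00 | 0.048–0.052 |
| AR(1) by visit, 0.5 | 0.81 | 0.060–0.063 |
| AR(1) by visit, 0.7 | 0.69 | 0.071–0.074 |
| AR(1) by visit, 0.9 | 0.58 | 0.078–0.081 |
| Decay 0.95 per week, visits at about weeks 0, 3, 5, 13, 26 | 0.59 | 0.077–0.084 |
| AR(1) 0.7, SDs rising from 1.2 to 2.5 | 0.66 | 0.074–0.075 |

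In all of these settings, the Greenhouse–Geisser-corrected test stayed at 0.044–0.051, the between-group main effect at 0.046–0.053, and the last-visit t-test at 0.048–0.052.

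**The case against.** The strongest reply is that silence is not a commitment. Section 7 does not say that incomplete participants will be excluded, nor that uncorrected p-values will be used. A reader might infer that the PNF comparison will be a completers' analysis with p-values that are too small. The documents do not support that:

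- The sphericity problem touches only the within-subject tests, only if sphericity fails, and only without a correction. The between-group main effect and the t-tests are unaffected.
- Listwise deletion costs precision, and it may bias the estimate in either direction, but it does not by itself shrink p-values.
- The planned t-tests can use everyone seen at a visit, so not every PNF comparison is limited to five-visit completers.
- Bias needs dropout that differs by arm. Both arms receive the same injections and the same number of sessions, so dropout may well be similar, and then the bias is about zero.
- The near-zero bias of the all-visits estimate follows from simulating dropout that depends only on observed pain, the condition under which such a method is unbiased.
- A Greenhouse–Geisser correction alone would settle the sphericity half.

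All of this stands, and it limits the claim. It does not remove it. The visit-wise t-tests do not rescue the plan: when participants leave for good, the 6-month t-test uses the same people as the completers' ANOVA and carries the same bias. A sphericity correction does nothing for missed visits. Differential dropout is neither stated nor ruled out.

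**Conclusion.** The concern holds in conditional form. The named ANOVA, applied in its classical form, discards every participant with a missed visit: about 8%, 19% or 34% at an assumed 2%, 5% or 10% missing per post-baseline visit. It biases the PNF comparison if dropout depends on pain differently by arm, by about 0.3 NRS points in the one-arm case and 0.5–0.7 in the opposite-direction case, under the assumed 40 per arm, SD 2, correlation 0.6 and 25–28% dropout. If sphericity fails and nothing is corrected, the group-by-time test runs at about 6–8% instead of 5%.

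The gap in section 7 and the listwise mechanism are certain. The sizes are illustrations, because the documents give none of the quantities that would fix them. The change is worth making because a better method is available at little cost, not because the plan has been shown to give a wrong answer.

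**What to change.** In section 7, replace repeated measures ANOVA with a REML mixed model for repeated measures for the comparison of PNF with conventional physiotherapy:

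- **Outcomes:** post-rehabilitation, 3-month and 6-month scores.
- **Fixed effects:** arm, visit, arm-by-visit, baseline score and baseline-by-visit.
- **Covariance and degrees of freedom:** unstructured; Kenward–Roger.
- **Participants:** analysed as allocated.
- **Post-injection score:** it precedes the divergence of the arms, so it can sharpen the comparison. Enter it as a further outcome with a common mean across arms, or impute it. Used as a plain covariate, a missing value would remove the participant and bring listwise deletion back. Entered as an outcome, it lets every randomised participant with a baseline and any later score contribute.
- **Primary test:** name one visit from post-rehabilitation onwards as primary, before any data are seen, and take the arm contrast at that visit.
- **Sensitivity analysis:** one delta-adjusted analysis at the primary visit, because the model relies on data being missing at random.
- **First part of the objective:** report within-group change from baseline separately.

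The cost is a few sentences in section 7 and slightly more analysis work in standard software. No new data are needed. The downside is reliance on the missing-at-random assumption, which the sensitivity analysis probes but cannot verify.

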## 5. Intervention

All participants receive 3 weekly ultrasound-guided subacromial corticosteroid injections (triamcinolone acetate 40 mg + lidocaine).

After injections:

- Experimental group: PNF-based rehabilitation (10 sessions, 2 weeks)
- Control group: Conventional physiotherapy (10 sessions, 2 weeks)

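### Four secondary outcomes behind the function and quality-of-life aims share one unadjusted p<0.05 rule, with no condition on NRS, testing order or exploratory label

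*Combined protocol and SAP*

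**What the plan says.** The comparative part of the objective (section 2) is "to compare PNF-based therapy with conventional physiotherapy in improving pain, function, and quality of life in patients with subacromial bursitis". Section 6 makes NRS the only primary outcome and lists four secondary outcomes: DASH, EQ-5D-3L, EQ-VAS and ROM. The visit schedule there is "Assessments at baseline, post-injection, post-rehabilitation, 3 months, and 6 months follow-up".

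Section 5 gives both arms the same injection course ("All participants receive 3 weekly ultrasound-guided subacromial corticosteroid injections"); the randomised programmes start only after it.

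Section 7 is two sentences long. The methods are given as "Data will be analyzed using repeated measures ANOVA and independent t-tests", and the decision rule as "A p-value $<0.05$ will be considered statistically significant". It does not say which method applies to which outcome or visit. No section states a testing order, a condition on the NRS result, an adjustment for the number of tests or an exploratory status for the secondary outcomes.

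**The concern.** Two of the three aims in the comparison rest wholly on secondary outcomes. On the natural mapping, function is measured by DASH and ROM, and quality of life by EQ-5D-3L and EQ-VAS. Each aim can therefore be met through either of two measures, and section 7 lets each be called significant at 0.05 on its own. Followed as written, one secondary p-value below 0.05 supports part of the stated objective even when NRS shows no difference.

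At stake is how far a reader can trust a statement that the programmes differ on function or quality of life. This is separate from the choice of visit or contrast for NRS, and it would remain after that choice is made.

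**Working it through.** The plan states no family-wise error rate, so there is no figure of its own to reproduce.

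**Inputs from the documents**
- Threshold per test: 0.05 (section 7). Sidedness is not stated; two-sided is assumed.
- Secondary outcomes: 4 (section 6). ROM counts once because no planes of movement are specified; testing several planes would raise the figures.
- Visits after the arms diverge: 3 of the 5 (end of rehabilitation, 3 months, 6 months), because the injections are common to both arms (sections 5 and 6).

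**Assumed input:** the correlation between test statistics, which the documents do not give. A range of 0 to 0.8 is shown.

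**Independent tests:** the chance of at least one false positive among k tests is 1 − 0.95^k.
- k = 2 (one aim, two measures, one visit): 1 − 0.95² = 9.75%
- k = 4 (one test per outcome): 1 − 0.95⁴ = 18.5%
- k = 12 (4 outcomes × 3 visits): 1 − 0.95¹² = 46.0%

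**Correlated tests:** with no arm difference, draw T_i = √ρ·Z₀ + √(1−ρ)·Z_i for i = 1 to k, with all Z standard normal, and count the draws in which any |T_i| exceeds 1.96. Simulation with at least 400,000 draws gives:

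| Tests | ρ = 0 | 0.3 | 0.5 | 0.7 | 0.8 |
|---|---|---|---|---|---|
| 2 | 9.75% | 9.5% | 9.1% | 8.4% | 7.8% |
| 4 | 18.5% | 17.4% | 15.6% | 13.0% | 11.4% |
| 12 | 46.0% | 39.8% | 32% | 23.2% | 18.5% |

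Allowing separate correlations between outcomes and between visits for the 12 tests gives 35.6% when both are 0.5, and 42.1% down to 21.2% as both run from 0.3 to 0.8. These lie inside the range in the last row.

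**Direction:** counting only results that favour PNF (T_i > 1.96), four tests give 8.8%, 7.8% and 6.5% at ρ = 0.3, 0.5 and 0.7. Twelve tests give 20.2%, 16.0% and 11.6%. That is about half the two-sided figure in each case.

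**Which row applies:** if each outcome is judged by one group-by-time test from the repeated measures ANOVA, or by one t-test at one visit, the four-test row applies. The twelve-test row needs a t-test of every outcome at all three visits. Section 7 does not exclude this, but does not say it either.

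**Check on the fixed-sequence option:** when testing stops at the first non-significant result, a false claim requires rejection of the first true null hypothesis in the order, which has probability at most 0.05. The error over the whole sequence is therefore at most 5%.

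**The case against.** The strongest reply is that section 6 already ranks the outcomes. NRS is primary, the rest are secondary, the NRS error rate is untouched, and no passage promises confirmatory secondary claims or family-wise control. Whether outcomes already labelled secondary need formal control is partly convention. This stands in part, and it is why the point does not threaten the primary result. But the label does not say what a secondary p-value below 0.05 may support, while section 2 names function and quality of life in the objective and section 7 calls any such p-value significant.

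Three stronger readings are tempting, and the documents do not support them.
- A reader might infer that the objective asserts that PNF improves function and quality of life. Section 2 sets out a comparison, not a claim of benefit.
- A reader might take 16% and 32% as properties of the plan. Both need an assumed common correlation of 0.5, and the second also needs visit-by-visit t-tests that section 7 does not specify.
- A reader might say that the error for each claim is three to six times the nominal 5% (15.6/5 = 3.1; 32/5 = 6.4). Those ratios describe the whole pool of secondary tests in both directions. One aim with two measures at one visit has about 9.1% at correlation 0.5, of which about 4.6% favours PNF.

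A fair objection to a sequential remedy is that it needs a primary NRS visit and contrast, which the plan does not define, and that the order of outcomes is the sponsor's choice. This stands, and the fix below allows for it.

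**Conclusion.** The concern holds in a limited form. With one unadjusted threshold across four secondary outcomes, the chance of at least one two-sided false positive is about 11% to 19% if each outcome is tested once (15.6% at correlation 0.5, 18.5% if independent). For either aim alone, with two measures at one visit, it is about 8% to 10%. It reaches about 19% to 46% (32% at correlation 0.5) only if every outcome is t-tested at all three visits after the arms diverge.

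These figures assume two-sided tests, no true difference between the arms, ROM counted as one variable and correlations between 0 and 0.8. The exact size depends on the correlation, but even the lowest four-test figure is more than twice 5%. It would be wrong to conclude that the primary NRS result is compromised; this point leaves it unaffected. What lacks error control is any confirmatory statement about function or quality of life.

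**What to change.** Main change: state in section 7 that the p<0.05 rule for confirmatory claims applies only to the primary NRS contrast. Report all secondary outcomes as exploratory, with estimates and 95% confidence intervals and no claim of significance, and limit the confirmatory claim in section 2 to pain.

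Option, if the sponsor wants confirmatory function and quality-of-life claims: first fix one primary NRS visit and contrast. Then test at that visit in a prespecified fixed sequence, each at two-sided 0.05, stopping at the first non-significant result. One example is NRS, then one function measure such as DASH, then one quality-of-life measure such as EQ-5D-3L. The remaining measures and visits stay exploratory.

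Cost: a few sentences in sections 2 and 7, with no extra patients, visits or data. The price is in the claims: under the exploratory label, function and quality of life cannot be called confirmed at all. Under the sequence, they can be confirmed only if NRS, and any measure placed before them, is also significant.
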